## 5.4 Safety Analysis Set

The Safety Analysis Set will include data from all subjects who receive any amount of study drug. Safety analysis will be based on the actual treatment received on Cycle 1 Day 1, which should be the assigned cohort. All data will be included, and no subjects excluded because of protocol violations.

## 5.5 Pharmacokinetics Analysis Set

The PK Analysis Set will include all subjects who have received study drug with available plasma concentrations and PK parameters for ASTX029.

## 5.6 Pharmacodynamic Analysis Set

Subjects will be included in the pharmacodynamic and biomarker analyses if they have received study drug and their samples were successfully collected and analyzed.

#### 6.0 SCHEDULE OF ANALYSES

Analysis will be conducted after all subjects have completed at least one RECIST assessment. The expected study duration is approximately 3.5 years (42 months), including approximately 36 months for recruitment and approximately 6 months for safety follow-up. The study started in Q2 2018.

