5.4.1. Discontinuation From Study Treatment

Subjects may permanently discontinue study treatment at any time (**note: subjects who experience disease progression while receiving ASTX029 should not remain on study treatment**). Subjects who discontinue study treatment will still continue study follow-up procedures until death, or until they withdraw consent or the study is closed. Investigators are encouraged to assess all subjects according to the study protocol even after discontinuation from study treatment. Possible reasons for discontinuation of study treatment include the following:

- Investigators can discontinue subjects from study treatment in case of unacceptable toxicity, non-compliance, disease progression requiring alternative therapy, or if the investigator determines it is in the subject's best interest.
- The Sponsor may require that a subject is discontinued from treatment for safety reasons or for noncompliance.

In all cases, the reason(s) for discontinuation from study treatment must be recorded in the source document and on the relevant page of the subject's electronic case report form (eCRF).

It is important to obtain protocol-specified follow-up information on any subject discontinued from study treatment. For subjects who discontinue study treatment, the investigator should review the follow-up procedures with the subject, including the number of visits, the specific procedures to be done, and the total length of the follow-up period. If at all possible, subjects should undergo all safety and preliminary clinical activity evaluations at the Tx Term visit (Section 9.4.13) and the 30-day Safety Follow-up visit (Section 9.4.14). Section 10 describes follow-up for AEs. At minimum, subjects should be followed up for safety until 30 days after the last dose of study treatment (see Section 10.3).

Subjects who agree to remain enrolled in the study after discontinuing study treatment and completing the 30-day Safety Follow-up visit will be contacted by telephone for health status information every 3 months until death, withdrawal of consent, or the end of study, whichever occurs first (see Section 9.4.15).

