9. STUDY ASSESSMENTS AND PROCEDURES

9.1. Preliminary Clinical Activity Assessments

Measurable disease according to RECIST v1.1 (Appendix 3) will be assessed using CT or MRI scans at baseline (screening), every 2 cycles (\pm 7 days) for the first 4 cycles, and then every 4 cycles (\pm 1 cycle) thereafter until clinical and/or radiographic disease progression, death, or the subject withdraws consent. Tumor markers (if applicable) should be measured at the same time points as the time points for radiological assessments.

For subjects whose disease is not measurable using RECIST v1.1, disease status must be reliably and consistently followed using another generally acceptable method.

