11.3. Schedule of Analyses

This is an open-label study. Ongoing analyses to help manage the study and support the DSRC reviews for safety and antitumor activity will be undertaken. A final analysis will be conducted after all subjects have completed the study.

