If a new lesion is equivocal, for example because of its small size, continued therapy and follow-up evaluation will clarify if it represents truly new disease. If repeat scans confirm there is definitely a new lesion, then progression should be declared using the date of the initial scan.

Evaluation of Best Overall Response

The best overall response is the best response recorded from the start of the study treatment until the end of treatment. No confirmatory measurement for CR, PR, or SD is required in the study.

The subject's best overall response assignment will depend on the findings of both target and nontarget disease and will also take into consideration the appearance of new lesions.

Time Point Response

Please follow the per-protocol time point response assessments. Table 14 below provides a summary of the overall response status calculation at each time point for subjects who have measurable disease at baseline.

Time Point Response: Subjects with Target (±Nontarget) Disease			
Target Lesions	Nontarget Lesions	New Lesions	Overall Response
CR	CR	No	CR
CR	Non-CR/Non-PD	No	PR
CR	Not evaluated	No	PR
PR	Non-PD or not all evaluated	No	PR
SD	Non-PD or not all evaluated	No	SD
Not all evaluated	Non-PD	No	NE
Pd	Any	Yes or No	PD
Any	PD	Yes or No	PD
Any	Any	Yes	PD

Table 14:Overall Response

CR=complete response, NE=inevaluable, PD=progressive disease, PR=partial response; SD=stable disease.

Missing Assessments and Inevaluable Designation

When no imaging/measurement is done at a particular time point, the subject is not evaluable at that time point. If only a subset of lesion measurements are made at an assessment, usually the case is also considered not evaluable at that time point, unless a convincing argument can be made that the contribution of the individual missing lesion(s) would not change the assigned time point response. This would be most likely to happen in the case of PD. For example, if a subject had a baseline sum of 50 mm with 3 measured lesions and at follow-up only 2 lesions were assessed, but those gave a sum of 80 mm, the subject will have achieved PD status, regardless of the contribution of the missing lesion.

Best Overall Response: All Time Points

The best overall response is determined once all the data for the subject is known.

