Best response determination in studies where confirmation of CR or PR is not required: Best response in these studies is defined as the best response across all time points (eg, if a subject has SD at first assessment, PR at second assessment, and PD on last assessment, he or she will have a best overall response of PR). When SD is believed to be best response, it must also meet the protocol-specified minimum time from baseline (6 weeks). If the minimum time is not met when SD is otherwise the best time point response, the subject's best response depends on the subsequent assessments. For example, if a subject has SD at first assessment, but PD at the second assessment, and does not the meet minimum duration for SD, he or she will have a best response of PD. The same subject lost to follow-up after the first SD assessment would be considered inevaluable.

Special Notes on Response Assessment

When nodal disease is included in the sum of target lesions and the nodes decrease to 'normal' size (<10 mm), they may still have a measurement reported on scans. This measurement should

be recorded even though the nodes are normal, in order not to overstate progression should it be based on increase in size of the nodes. As noted earlier, this means that subjects with CR may not have a total sum of 'zero' on the eCRF.

Subjects with a global deterioration of health status requiring discontinuation of treatment without objective evidence of disease progression at that time should be reported as 'symptomatic deterioration.' Every effort should be made to document objective progression even after discontinuation of treatment. Symptomatic deterioration is not a descriptor of an objective response: it is a reason for stopping study therapy. The objective response status of such subjects is to be determined by evaluation of target and nontarget disease.

For equivocal findings of progression (eg, very small and uncertain new lesions; cystic changes or necrosis in existing lesions), treatment may continue until the next scheduled assessment. If at the next scheduled assessment, progression is confirmed, the date of progression should be the earlier date when progression was suspected.

Frequency of Tumor Re-evaluation

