## 7.5.1 Overall Response and Disease Control Rate

The ORR will be calculated as the number of evaluable subjects whose best response is CR or PR, divided by the total number of subjects evaluable for ORR analysis (Section 5.3). The DCR will be calculated as the number of subjects whose best response is CR, PR, or SD, divided by the total number of subjects evaluable for DCR analysis (Section 5.3). The 90% Clopper-Pearson CIs for the ORR and DCR will be provided.

Best response for a subject is defined as the best overall response from all post baseline assessments of a subject in the study. When SD is believed to be the best response, it must also meet the protocol-specified minimum time from baseline (6 weeks). If the minimum time is not met when SD is otherwise the best time point response, the subject's best response depends on the subsequent assessments.

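### The SAP names no data cut for the Phase 2 primary ORR beyond a one-scan floor, and its best-response window is open where the protocol appendix closes it at end of treatment; both effects are probably small.

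*SAP*

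**What the plan says.** **When the analysis happens.** SAP 6.0: "Analysis will be conducted after all subjects have completed at least one RECIST assessment". Protocol 11.3 provides for ongoing analyses to support the DSRC and then says: "A final analysis will be conducted after all subjects have completed the study". SAP 1.0 states that its analyses supersede the protocol's high-level plan. SAP 7.9 (Changes from Protocol) mentions neither analysis timing nor the best-response window.

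**Which scans count.** SAP 7.5.1: "Best response for a subject is defined as the best overall response from all post baseline assessments of a subject in the study". Its only time condition is the 6-week minimum for stable disease. Protocol Appendix 3, to which SAP 7.5 refers for RECIST details, has two wordings. One is "The best overall response is the best response recorded from the start of the study treatment until the end of treatment"; the other, under the all-time-points heading, is "Best response in these studies is defined as the best response across all time points". Appendix 3 also says: "No confirmatory measurement for CR, PR, or SD is required in the study".

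**When scanning stops.** Protocol 9.1 continues scans "until clinical and/or radiographic disease progression, death, or the subject withdraws consent". New anticancer therapy is not in that list, although it ends scanning in the extension-phase schedule (Protocol Table 13). Protocol 5.4.1 adds: "Investigators are encouraged to assess all subjects according to the study protocol even after discontinuation from study treatment".

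**The concern.** ORR is the Phase 2 primary endpoint, and each cohort is judged on a count of at least 6 responses in 29. Two rules decide which responses enter that count, and the SAP leaves both loose.

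- **Cut-off.** One RECIST assessment per subject can be met at about week 6. A response first seen at the week 12 or week 24 scan would be missed in subjects enrolled shortly before the cut.
- **Window.** A response seen after another anticancer therapy has started is not excluded, and a single unconfirmed scan is enough to count.

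The study is open-label with investigator-assessed response and ongoing review of activity data. Unless these rules are fixed in writing before the cut, they could be settled with the responses already known.

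**Working it through.** **Inputs from the documents.** Simon design (SAP 4.0): 10 then 19 subjects; continue on at least 2 of 10; reject on at least 6 of 29; p0 = 0.10, p1 = 0.30. Cycles of 21 days, with scans after Cycles 2 and 4 and then every 4 cycles ±1 cycle (Protocol 9.1 and Table 11). Study start in Q2 2018 (SAP 6.0). SAP V1.0 approved 2 April 2024. Planned recruitment of 55 months within 61 months (Protocol 12).

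**1. Reproduce the design.** P(reject | p) = Σ over x = 2..10 of Bin(x; 10, p) × P(Bin(19, p) ≥ 6 − x).
- p = 0.10: 0.0471 (stated limit 0.05).
- p = 0.30: 0.8051 (stated 80%).

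The sample size is correct and is not in question.

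**2. Scan times.** 2 × 3 = week 6; 4 × 3 = week 12; 8 × 3 = week 24 (weeks 21 to 27 with the window). From the SAP's floor to the third scan is 24 − 6 = 18 weeks.

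**3. Does the calendar settle the cut?**
- The SAP's own 42 months from Q2 2018 end in Q4 2021, before the SAP was approved, so they fix no cut-off.
- The protocol's 55 months from Q2 2018 end between about November 2022 and January 2023. Adding 24 weeks gives roughly mid-2023, still before 2 April 2024. If that plan held, every subject was past week 24 by SAP approval. Actual accrual is not shown.

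**4. How much could an early cut cost?** The documents give no response timing and no Phase 2 accrual rate, so these are assumptions: Stage 1 mature; 19 Stage 2 subjects evenly spaced; cut at last entry + 6 weeks; first responses split over weeks 6/12/24 as 70/20/10 or 50/30/20, with none later. Each Stage 2 subject's response probability is 0.30 times the share visible at the cut, and the exact distribution of their sum replaces Bin(19, p) in step 1.

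| Stage 2 accrual | Under 24 weeks at cut | Power, 70/20/10 | Power, 50/30/20 |
|---|---|---|---|
| 13 weeks | 19 of 19 | 0.741 | 0.658 |
| 26 weeks | 13 of 19 | 0.771 | 0.732 |
| 52 weeks | 7 of 19 | 0.788 | 0.772 |
| 90 weeks | 4 of 19 | 0.795 | 0.787 |

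A cut at last entry + 24 weeks gives 0.805 in every row.

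**5. How much could the open window cost?** If a share m of true non-responders were credited with another therapy's response, the observed rate at p0 would be 0.10 + 0.90m. The documents give no m.

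| Assumed m | Observed rate | Type I error, both stages affected | Type I error, Stage 2 only |
|---|---|---|---|
| 0.5% | 0.1045 | 0.056 | 0.052 |
| 1% | 0.109 | 0.066 | 0.056 |

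The Stage 2 column is the more natural one, because a response after new therapy would often come after the Stage 1 decision.

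**6. One-subject sensitivity (no timing assumption).** At p = 0.10, P(pass Stage 1 and finish on exactly 5) = 0.0545, which is 0.0545 / 0.2639 = 21% of cohorts reaching Stage 2. One wrongly credited subject would turn these into rejections. At p = 0.30, P(pass Stage 1 and finish on exactly 6) = 0.0662, where one missed responder would do the reverse.

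**The case against.** **On the cut-off.** A reader might infer that SAP 6.0 cancels the protocol's final analysis. The text does not say that. At least one assessment is a floor, Protocol 11.3 speaks of a final analysis, and the two can coexist. Late responders would then be captured at the final analysis. This stands, and it reduces the fault to an unnamed cut. But the SAP claims precedence, gives no other trigger, and does not say which analysis yields the primary ORR. The planned calendar also suggests mature data. It is a plan rather than a record of accrual, and the roughly 6 months allowed after recruitment are for safety follow-up, not a condition for analysis.

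**On the window.** A reader might infer that responses after progression will be counted. Few such scans should exist: subjects who progress should not stay on drug (Protocol 5.4.1), scheduled scanning stops at progression, and long-term follow-up is by telephone for survival and progression date (Protocol 9.4.15). The Treatment Termination visit is to precede new therapy (Protocol 9.4.13). All of this stands. What remains is the subject who stops drug without progression, starts other therapy and is still scanned. The cross-reference to Appendix 3 does not close that route, because Appendix 3 carries two wordings.

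**On size.** That one subject can tip 5 to 6 is true of any rule of this size and is not itself a fault. It shows only why the counting rules need to be exact.

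**Conclusion.** The point holds as two loose definitions for the primary endpoint. SAP 6.0 permits an ORR analysis after one scan per subject without saying how it relates to Protocol 11.3. SAP 7.5.1 conflicts with the end-of-treatment wording in Appendix 3.

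The likely effect is small. Power of 0.772 to 0.795 against 0.805 rests on a cut at exactly last entry + 6 weeks, accrual over 52 to 90 weeks and the assumed response timing. The 0.658 figure needs 19 molecularly selected subjects in one cohort within 13 weeks and half of responders appearing late; it should not be read as the expected loss. The type I error figures of 0.052 to 0.066 rest wholly on assumed miscredit rates and illustrate direction only.

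The documents do not show that any cohort was cut early or any response miscredited. Severity: minor to should-fix, with moderate confidence.

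**What to change.** - **SAP 6.0.** Name the primary ORR cut-off. Require that every treated subject has had the scheduled scans through the third (about week 24), or has earlier progressed, died, started new anticancer therapy, stopped assessments or withdrawn. This also covers subjects who die before a first scan and so can never meet the present trigger. Alternatively, state that the primary ORR comes from the Protocol 11.3 final analysis.
- **SAP 7.5.1.** Count only assessments up to the earlier of first documented progression or start of new anticancer therapy, and say that a Treatment Termination scan taken before new therapy counts. This matches neither Appendix 3 wording exactly, so reconcile all three.
- **SAP 7.9.** List any departure from the protocol that remains.

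**Cost.** SAP wording, with no extra subjects or scans. If Appendix 3 itself is edited, that is a protocol change to be handled under Protocol 14.4. The week 24 option delays readout by up to about 18 weeks beyond the SAP's floor; the Protocol 11.3 option could take longer. ORR may be slightly lower if any scan after progression or new therapy drops out.

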#### 7.0 STATISTICAL ANALYSIS

Unless otherwise specified, all statistical tests and confidence intervals (CIs) described in this document will be two-sided with alpha 0.05. Data summaries and listings will be generated using SAS version 9.4 or a more recent version (SAS Institute Inc., Cary, NC, USA).

The first dosing date is defined as the first date the subject received any study drug.

Analysis tables will be summarized by cohorts and all cohorts combined for phase 1 part A, phase 1 part B and phase 2 unless specified otherwise. For example,

- Phase 1A: Cohort 1, Cohort 2, ..., Cohort n
- Phase 1B powder in bottle and tablets
- Phase 2: Cohort A, Cohort B, ..., Cohort F
- Phase 1A, Phase 1B, and Phase 2

Tables may be combined and/or separated as allowed by number of cohorts.

The AEs will be summarized by assigned cohort at the onset of the AE (Section 7.6.2). Efficacy analyses, laboratory tests, vital signs, electrocardiogram (ECG), and Eastern Cooperative

Oncology Group (ECOG) performance status will be summarized by assigned cohort and all subjects combined (Total), unless otherwise specified.

The following will be summarized by assigned cohort and all subjects combined (Total), unless otherwise specified:

- · Efficacy analyses,
- Treatment emergent adverse events (TEAEs),
- · Laboratory tests,
- Vital signs,
- Electrocardiogram (ECG), and
- Eastern Cooperative Oncology Group (ECOG) performance status.

The following data listings by subject identification (ID) number (which includes the study center number) will be provided:

- All enrolled subjects
- Screen failure subjects (with reason for screen failure)
- Disposition (with reason(s) for discontinuation of treatment and withdrawal from study)
- Protocol deviations
- Demographic and baseline characteristics
- Study drug administration
- Individual efficacy data
- Subjects excluded from the efficacy analysis
- TEAEs
- Deaths (including primary cause of death)
- Serious adverse events (SAEs)
- Other significant TEAEs (including treatment discontinuation due to AEs)
- Concomitant medications

### • Selected laboratory measurements

Additional data listings may be generated to support other relevant discussions in the clinical study report.

Generally, all tables/figures presented will be supported by a listing of the data summarized in table/figure.

Taiho/Biostatistics and Data Management (BDM) and Clinical Data Interchange Standards Consortium (CDISC) standards will be followed.

## 7.1 Subject Disposition

Subject disposition including number of subjects enrolled, treated, and discontinued from study drug by reason, as well as reasons for withdrawal from study (ie, death, complete consent withdrawal, or lost to follow-up) and subjects ongoing at data-cut will be summarized using frequencies and percentages based on information collected on the study electronic case report form (eCRF). Subjects in the All-Subject Analysis Set (Section Error! Reference source not found.) will be included in the disposition analysis.

## 7.2 Demographic and Other Baseline Characteristics

Subject demographic and baseline characteristics will be summarized by mean, standard deviation, median, minimum, and maximum for continuous variables; and by counts and percentages for categorical variables. For the Safety Analysis Set (section 5.4), all subjects who received any amount of study drug will be included in the analysis of demographic and baseline characteristics.

Summaries will be provided separately for each regimen in Phase 1 Part A, for the RDE cohort(s) in Phase 1 Part B, and for each cohort in Phase 2.

The demographic variables include age, age category ((<18, 18 <65, 65 <75, ≥75 years), sex, ethnicity, and race. Baseline characteristics may include height, weight, ECOG performance status, prior anti-cancer therapy, and best responses to prior therapy.

Baseline is defined as the last value(s) available before or on the 1st dosing date unless otherwise specified.

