9.4.11. Treatment and Follow-up Procedures

The first day of study drug administration is C1D1. Consecutive QD oral doses of study drug will be administered (or self-administered) on Days 1 to 21 (Regimen 1) or Days 1 to 14 (Regimen 2). For details on study drug administration please refer to Section 7.1.7. Subjects should drink 1 full glass of water immediately after drug ingestion and not lay down for at least 30 minutes after drug ingestion. On scheduled visit days, subjects should wait to take the study drug until after they have checked into the study center and undergone the predose procedures. Subjects should record the time and date of each dose they self-administer in their dosing diary.

Treatment and follow-up procedures will be followed for Regimen 1 or 2, based on the regimen selected.

9.4.11.1. Cycle 1 – Week 1

Week 1 is a dosing week in both Regimen 1 and Regimen 2: consecutive QD oral doses of study treatment will be administered (or self-administered) on Days 1 to 7.

9.4.11.1.1. Cycle 1 – Week 1 – Day 1

Before administration of study treatment:

- Perform symptom-directed PE (Section 9.4.1).
- Record subject's weight.
- Record vital signs (Section 9.4.2).
- Evaluate ECOG performance status (Appendix 1).
- Perform predose 12-lead ECG in triplicate (Section 9.4.4). Note: ECG findings must meet study entry criteria before dosing.
- Record screening procedure-related AEs that occur before the start of study treatment and concomitant medications received since screening.
- Collect blood samples for hematology, coagulation, and serum chemistry laboratory tests and review results; collect urine sample for urinalysis (Table 10). Note: hematology and chemistry values must meet study entry criteria before dosing, C1D1 hematology, coagulation, serum chemistry, and urine evaluations do not need to be repeated if screening tests are done within 4 days prior to first dose of ASTX029, and these tests may be performed on the day before the visit if more convenient.
- Perform serum or urine pregnancy test for women of child-bearing potential only, and this test may be performed within 24 hours before the start of study treatment if more convenient.
- Collect predose blood sample for PK analysis (Section 9.2.1, Table 4, Table 5, Table 6, and Table 7).

- Collect predose blood sample for ctDNA (Section 9.2.2, Table 8).
- Confirm eligibility.

Subject ingests study treatment while at the clinic.

After administration of study treatment:

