- Record blood pressure and heart rate 1 hour (± 30 minutes) postdose (Section 9.4.2).
- Perform 12-lead ECG in triplicate 2 hours (± 30 minutes) postdose (Section 9.4.4).
- Record AEs and concomitant medications.
- Collect blood samples for postdose PK analysis (Section 9.2.1, Table 4, Table 5, Table 6, and Table 7).
- Dispense study treatment (ASTX029), provide instruction for self-administration, and instruct subject to, on dosing days when there is a scheduled visit, refrain from ingesting the study drug until after being on-site at the study clinic and the predose study procedures have been performed.
- Provide a dosing diary to the subject and instructions for how to enter dosing information.

9.4.11.1.2. Cycle 1 – Week 1 – Day 2

Before administration of study treatment:

- Record vital signs (Section 9.4.2).
- Perform predose 12-lead ECG in triplicate (Section 9.4.4).
- Record AEs and concomitant medications.
- Collect post C1D1 dose blood sample for PK analysis (Section 9.2.1, Table 4, Table 5, Table 6, and Table 7).

Subject ingests study treatment while at the clinic.

After administration of study treatment:

• Record AEs and concomitant medications.

9.4.11.2. Cycle 1 – Week 2 – Day 8

Week 2 is a dosing week in both Regimen 1 and Regimen 2: consecutive QD oral doses of study treatment will be administered (or self-administered) on Days 8 to 14.

Before administration of study treatment (note: hematology and serum chemistry tests may be performed on the day before the visit if more convenient):

- Perform symptom-directed PE (Section 9.4.1).
- Record vital signs (Section 9.4.2).
- Evaluate ECOG performance status (Appendix 1).

- Record AEs and concomitant medications.
- Perform predose 12-lead ECG in triplicate (Section 9.4.4).
- Collect blood samples for hematology and serum chemistry laboratory tests (Table 10).

Subject ingests study treatment while at the clinic.

After administration of study treatment:

- Record AEs and concomitant medications.
- Review dosing diary to assess dosing compliance.
- Dispense study treatment (ASTX029), provide instruction for self-administration as needed, and instruct subject to, on dosing days when there is a scheduled visit, refrain from ingesting the study drug until after being are on-site at the study clinic and the predose study procedures have been performed.

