## 7.6.8 Electrocardiogram (ECG)

The 12-lead ECGs will be performed at screening and predose and 2 hours (±30 minutes) postdose on C1D1 and C2D1; they will be performed predose at all other time points on the dosing days and at the Treatment Termination visit as indicated. For each ECG parameter (heart rate, RR interval, PR interval, QRS duration, QT interval, and QT corrected for heart rate using Fridericia's formula (QTcF)), the mean of the available triplicate ECG values will be calculated.

ECG findings will be listed by subject and, if data permit, may be summarized as follows:

- The values and respective changes from baseline may be summarized by visit.
- Summaries may also be provided of the maximum post-baseline absolute QTcF and the maximum post-baseline increase in QTcF.

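### The SAP sets baseline by calendar date, so read literally the on-drug 2-hour ECG on Cycle 1 Day 1 becomes the baseline for the QTcF change summaries

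*SAP*

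**What the plan says.** The only baseline definition in the SAP is in section 7.2: "Baseline is defined as the last value(s) available before or on the 1st dosing date unless otherwise specified". Section 7.0 fixes the date it refers to: "The first dosing date is defined as the first date the subject received any study drug". Neither sentence mentions a clock time or a predose condition.

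SAP 7.6.8 gives the ECG schedule: "The 12-lead ECGs will be performed at screening and predose and 2 hours (±30 minutes) postdose on C1D1 and C2D1"; otherwise "they will be performed predose at all other time points on the dosing days". Protocol 9.4.11.1.1 confirms both C1D1 recordings. Before dosing it says "Perform predose 12-lead ECG in triplicate (Section 9.4.4). Note: ECG findings must meet study entry criteria before dosing", and after dosing it calls for a second triplicate at 2 hours. Protocol 4.1.2 places the first dose on C1D1.

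SAP 7.6.8 averages each triplicate and then allows two kinds of summary: "The values and respective changes from baseline may be summarized by visit", and "Summaries may also be provided of the maximum post-baseline absolute QTcF and the maximum post-baseline increase in QTcF". It does not redefine baseline.

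**The concern.** The first dosing date holds two ECG time points, one off drug and one on drug. A rule that takes the last value up to and including that date selects the on-drug one. The exception in SAP 7.2 for cases specified elsewhere does not help, because no other section specifies an ECG baseline.

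Two things would then go wrong in the same tables:

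- Any QTcF effect already present 2 hours after the first dose is subtracted from every later value. The 2-hour change on C2D1 shrinks, and predose visits can show apparent shortening.
- The C1D1 2-hour ECG stops being post-baseline, so it drops out of both the maximum QTcF and the maximum increase.

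Both errors point towards reassurance. That matters in a first-in-human study whose protocol reports hERG inhibition (1.3.2.3), names potential arrhythmias as a risk (section 8) and excludes subjects with a QTc of 470 msec or more at screening (5.3).

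**Working it through.** **1. Apply the rule to the schedule.** ECGs up to and including the first dosing date, in order: screening, C1D1 predose, C1D1 2 hours postdose. The last is the 2-hour postdose triplicate, so it is the baseline under the literal rule.

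**2. Count what is lost.** SAP 7.9 says only Regimen 1 was opened. Its scheduled postdose ECGs fall on C1D1 and C2D1 only. One of these 2 becomes baseline, leaving 1. A subject who stops before C2D1 has no scheduled postdose QTcF change at all.

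**3. Size of the error in general.** Let d be the QTcF shift from C1D1 predose to 2 hours postdose, and e the change from C1D1 predose to a later time point. A predose baseline reports e; the literal rule reports e − d. This needs no assumption about the drug.

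- Same effect on C2D1 (e = d): reported 0, should be d.
- Larger effect on C2D1 (e = 1.5d): reported 0.5d, should be 1.5d.

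**4. Illustration with assumed kinetics.** The documents give no human QTcF effect and state no human half-life outright. Assume that the effect is proportional to plasma concentration, that concentration declines mono-exponentially from 2 hours, that dosing is once daily, and that steady state is reached by C2D1. Protocol 5.2, criterion 8, equates 32 days with about 5 half-lives of drug or metabolite plus 30 days. This implies a half-life of (32 − 30) × 24 / 5 = 9.6 h. If 5 half-lives were nearer 1 day (an assumption), the half-life would be 24 / 5 = 4.8 h.

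For half-life t, accumulation is R = 1 / (1 − 2^(−24/t)). The fraction left at the next predose ECG, 22 hours after the 2-hour point, is f = 2^(−22/t).

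| Quantity | t = 9.6 h | t = 4.8 h |
|---|---|---|
| R | 1.215 | 1.032 |
| f | 0.204 | 0.042 |
| C2D1 2-hour change, predose baseline (R·d) | 1.215d | 1.032d |
| C2D1 2-hour change, literal rule ((R − 1)·d) | 0.215d | 0.032d |
| Steady-state predose change, predose baseline (R·f·d) | 0.248d | 0.043d |
| Steady-state predose change, literal rule ((R·f − 1)·d) | −0.752d | −0.957d |

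**5. In milliseconds, for assumed values of d (C2D1, 2 hours):**

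| Assumed d | Literal rule | Predose baseline |
|---|---|---|
| 5 ms | 0.2 to 1.1 | 5.2 to 6.1 |
| 10 ms | 0.3 to 2.1 | 10.3 to 12.1 |
| 20 ms | 0.6 to 4.3 | 20.6 to 24.3 |

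For d = 10 ms, steady-state predose visits would show −9.6 to −7.5 ms instead of +0.4 to +2.5 ms.

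**6. Check whether other data are affected.** C1D1 laboratory tests and ECOG status are collected before dosing (Protocol 9.4.11.1.1), so their shift tables are sound on schedule. Vital signs do have a 1-hour postdose reading on C1D1, but SAP 7.6.7 summarizes them against fixed thresholds without a baseline. The problem is confined to ECG, where it reaches the other intervals in the by-visit change table as well as QTcF.

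**The case against.** The strongest case against is one of weight and intent.

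- **Optional output.** The ECG summaries depend on the data permitting and are worded as possibilities. No endpoint, DLT criterion or escalation rule uses QTcF change. This is true, and it limits the importance of the point.
- **Another safeguard.** Protocol 9.4.4 and 9.3.1 make a clinically significant ECG abnormality after the start of treatment an adverse event. Such a finding at 2 hours on C1D1 would therefore reach the TEAE tables whatever the baseline. That is also true, but it does not correct the change tables, and shifts below clinical significance would not be caught. It also shows the protocol treating as on-treatment the tracing that the SAP rule makes baseline.
- **Intent.** The rule sits in the demographics section, SAP 7.0 invokes company and CDISC standards, and SAP 1.0 places table specifications in a separate document. A programmer might well use the predose ECG. But 7.2 is the SAP's only baseline rule, sections 7.6.6, 7.6.8 and 7.6.9 rely on the word without redefining it, and nothing in the two documents states a predose condition.
- **Magnitude.** The half-life comes from a contraception window that may reflect a metabolite, the kinetic model is simple, and the millisecond effects are assumed. Protocol 1.3.2.3 reports no QTc prolongation in the dog study and considers free drug unlikely to approach the hERG IC50 of 11 µM. If d is near zero, so is the error. This stands: the figures are illustrations, and only e − d is established.
- **Remaining data.** Predose ECGs on C1D2, C1D8, C1D15 and later visits stay post-baseline, so a subject who stops early may still have some changes. These are measured from the disputed baseline, and none is postdose.

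**Conclusion.** The rule is wrong as written. Applied literally, it makes an on-drug ECG the baseline, biases every later ECG change by −d, and removes 1 of 2 scheduled postdose ECGs from the maximum QTcF summaries. These results follow from the SAP text and the visit schedule alone. The size in milliseconds cannot be derived from the documents. The tabulated values rest on the assumed half-lives, the proportional-effect model and the assumed d.

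The consequences are limited to optional, descriptive safety tables. By-subject listings and absolute values by visit are unaffected, as are the primary endpoints, sample size and error rates. It should be corrected before the ECG tables are programmed.

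**What to change.** Add to SAP 7.6.8: *For ECG, baseline is the mean of the predose C1D1 triplicate, or the last screening ECG if the predose ECG is missing; the C1D1 2-hour postdose ECG is post-baseline.*

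Add to SAP 7.2: *A value collected on the first dosing date counts as baseline only if it was taken before the first dose, by recorded time or, when no time is recorded, by its scheduled predose time point.*

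The first sentence resolves the ECG problem by itself. The second closes the gap in the general rule for any other measure taken after dosing on that day. The cost is two sentences. The predose C1D1 triplicate is already scheduled, and no new data are needed.
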